Strong evidence for what works for improving SRH outcomes among adolescent in resource-poor, but high disease burden settings remains poor despite the plethora of studies and investments into SRH programming. For example, guidelines in a 2016 WHO review of recommendations for care of HIV-positive youth were based on “low” and “very low” quality evidence, strongly suggesting the need for greater research.¹⁶ Similarly, in a recent report, the Institute of Medicine concluded that there is a lack of evidence for effective models of adolescent health care and a need for further research, particularly on how health services are delivered and by whom.¹⁷ Although a systematic review of sports-based HIV prevention programs (SBHP) has found evidence for effects on a range of social and behavioral outcomes (i.e., reduced stigma, increased self-efficacy, HIV-related knowledge, uptake of HIV testing a counselling (HTC), and condom use)¹⁸, rigorous evaluations that can attribute causality and verify pathways for change are lacking.^{18,19} As mentioned previously, GRS has already been rolling out a validated SKILLZ girl curriculum. In collaboration with their team, we have developed an enhanced curriculum which includes a comprehensive module on HIV self-testing, contraceptive choices and pre-exposure prophylaxis (PrEP) combined with increased access to these services through an enhanced soccer event.

In this study, we are proposing a pragmatic trial (based on real-world implementation) that will provide a robust evaluation of effectiveness and cost-effectiveness (CE) between a standard SKILLZ- girl curriculum, that has been delivered in many Lusaka secondary schools already, and a more robust, integrated, enhanced approach that includes additional SRH service offerings, including HIVST, PrEP and an expanded contraceptive method mix.

3. Rationale/Justification

a. Contribution of the study to science or body of knowledge

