The SKILLZ Adolescent SRH program (SKILLZ Package) aims to improve uptake of HIV testing, treatment and adherence and SRH services among adolescent girls. The model focuses on removing barriers to critical services by creating a fun, interactive environment for meaningful discussions and reflection (see **Figure1**).

Designed to be integrated into both secondary school education and clinical services, the SKILLZ Package is unique in that it offers holistic and continued support to adolescent girls through several avenues. First, it focuses on agency and empowerment by providing mentorship as well as accurate sexual health information with a trained age-peer coach. Second, the SKILLZ Package provides direct linkages to facility-based, youth-friendly care, leveraging existing community- and facility-based resources. Third, the SKILLZ Package ensures that comprehensive sexual and reproductive health education and services are

continuously given, including a focus on pregnancy and HIV prevention, the two largest risks that adolescent girls face in their pursuit of security and independence in adulthood.

The SKILLZ Package entails three integrated programs that work together to build a continuous support system that not only encourages uptake of contraceptive and HIV services, but also adherence and continued engagement with health services over the long-term (whether to contraceptive methods, HIV repeat testing, preventive services such as PREP and/or HIV treatment and care).

1. **SKILLZ-Girl** is a school-based program that provides adolescent girls (aged 16 and over regardless of HIV status) with a 10-12-week, soccer-based comprehensive sexuality and SRH education curriculum; gender and power dynamics in relationships are also addressed. This program is run during extra-curricular hours as part of the school syllabus. The program culminates in a soccer tournament where girls are provided the opportunity to access community-based SRH services offered at mobile clinics, including testing for HIV. The program was originally piloted in Zambia in 2015. Permission to continue to run the program was most recently granted in 2019 by the MOGE

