Within SKILLZ-Girl and SKILLZ-Club, our study will examine the additional benefits of offering access to two new health service offerings that are expressly designed to overcome barriers to uptake especially difficult for adolescents to overcome—HIV self-testing (HIVST) kits and access to an expanded method mix for contraceptive methods. Referral for contraceptive and SRH services will be made to the PEPFAR-funded DREAMS Houses or youth corners at local government facilities which are located within close distance to all schools where the SKILLZ package will be implemented.

Our mixed-methods evaluation will assess the effects of the enhanced SKILLZ offering (SKILLZ-Girl Enhanced & SKILLZ Club programs) compared to the SOC SKILLZ offering of SKILLZ-Girl only. Although the SKILLZ Program (Enhanced or SOC pending school allocation) will be offered to all girls enrolled in Grade 10 at selected study secondary schools, only girls aged 16 and over at the commencement of SKILLZ-Girl will be enrolled into the research study.

We will examine outcomes for school girls aged 16 and over enrolled in Grade 10 at the start of the intervention in up to 16 schools where the SOC SKILLZ Package is offered, compared to outcomes in up to 16 schools where the enhanced SKILLZ-Package is offered, including HIVST, the availability of expanded contraceptive services and the SKILLZ-Club following completion of SKILLZ-Girl. Therefore, all schools will be preassigned prior to the intervention into the following 2 categories (see **Figure 3** in *Section 8 - Methodology* below).

1. **SOC:** SKILLZ-Girl → Club SOC
2. **ENHANCED:** SKILLZ-Girl enhanced → SKILLZ-Club

Our central hypothesis is that the additional offering of HIVST and contraceptive services in an enhanced SKILLZ-Girl combined with the SKILLZ-Club offering will increase HIV testing and contraceptive uptake and continuation.

In addition to SKILLZ-Girl and SKILLZ-Club, girls testing HIV-positive at any time during the study intervention period will be additionally offered to participate in the SKILLZ-Plus facility-based curriculum for HIV-infected adolescents. The effect of the SKILLZ-Plus curriculum will be tested using a SmartCare-derived matched (i.e., on clinic, age, ART start date and gender) population.

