GRS has shown that soccer-based interventions combined with strong school and community partnerships and referral networks can change behaviors and make a significant impact on the health of young people.⁵³ In 2009 in South Africa, GRS piloted the SKILLZ-Girl program which addresses the unique needs of young women and adolescent girls. This program was then scaled in South Africa and expanded further into 13 countries in SSA. A recent evaluation of the SKILLZ-Girl program showed that participants significantly improved their knowledge and attitudes surrounding HIV risk for young women, negotiation skills, and sense of self-efficacy. In fact, 68.5% of girls that participated in the SKILLZ-Girl program underwent testing for HIV at the conclusion of the school-based curriculum.⁵⁴ Although SKILLZ-Girl has now served over 26,000 girls in 14 countries, it has never been rigorously evaluated for cost effectiveness and effectiveness.

6. Research questions

Our mixed-methods evaluation aims to assess the effect of the enhanced SKILLZ- girl on HIV testing and SRH related prevention services uptake (Aim 1), the effect of SKILLZ-Plus on HIV retention to care and VLS amongst HIV-infected girls (Aim 2) and identify mediating pathways and moderating factors leading to observed effects (Aim 3). Aim 3 will also assess the cost-effectiveness of the SKILLZ Package.

Our research questions are thus:

- a. What is the impact of enhanced SKILLZ-Girl vs regular SKILL-girl curriculum on HIV testing uptake among adolescent girls (aged 16 and over) over a 24-month period?
- b. What is the impact of enhanced SKILLZ-Club on HIV testing uptake among adolescent girls (aged 16 and over) over a 24-month period?
- c. Among HIV-positive adolescent girls, what is the impact of the SKILLZ-Plus intervention on:
 - a. retention in care and treatment at 6, 12, and 24 months
 - b. viral load suppression at 12 months?

- d. What specific barriers to access to services do the SKILLZ interventions (SKILLZ Girl, enhanced SKILLZ-girl, SKILLZ-Club & Plus) overcome?
- e. What are the mediators of the observed effects?
- f. What are the moderators of the observed effects?
- g. To what degree was the intervention implemented per protocol (fidelity)?
- h. What is the short- and long-term cost-effectiveness of the SKILLZ Package intervention?

7. Research aim(s)/General Objective and Specific Objectives

Aim 1: Assess the impact of SKILLZ over two years on:

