- (i) (a) **HIV testing** and (b) SRH-related prevention services uptake among adolescent girls aged 16-19 in up to 9 intervention schools (with enhanced HIVST, PrEP, and contraceptive method offerings) compared to up to 9 control schools using a quasi-experimental difference-in-difference approach; and
- (ii) **linkage to care and treatment, and viral load suppression and retention at 6, 12, and 24 months** through a cohort model using pre-existing SmartCare data on HIV+ individuals in care to match to adolescent girls aged 16 and over from the same district (Lusaka) who are identified to be HIV+ at any time during SKILLZ Girl or SKILLZ Club participation and enrolled in SKILLZ-Plus.

This will be achieved by i) using a quasi-experimental difference-in-difference approach that compares girls aged 16 and over in 9 SKILLZ control schools compared to 9 schools where enhanced SKILLZ will be delivered with the enhanced HIVST and a variety of contraceptive method offerings; and ii) through a cohort model using pre-existing SmartCare data on HIV+ individuals in care to match to adolescent girls aged 16 and over from the same district (Lusaka) who are identified to be HIV+ at any time during SKILLZ-Girl or SKILLZ-Club participation.

Aim 2: Examine how the intervention works including lessons learned for future implementation by

- (i) conducting a process evaluation to identify mediators, predictors, and barriers to uptake of the SKILLZ-Girl, Club, and Plus curricula both quantitatively through mediation and moderation analyses and qualitatively through a sequential explanatory approach using focus groups discussions, interviews and observation with coaches and girls; and by
- (ii) monitoring fidelity

Aim 3: Estimate the short- and long-term cost-effectiveness and return on investment of the SKILLZ Girl, Club, and Plus curricula for improving health outcomes for adolescent girls.

8. Methodology

a. Study design

We will conduct a mixed-methods evaluation of the SKILLZ intervention using the following approaches:

A **quasi-experimental cohort** of school-aged 16-year old and over females to be followed for a two-year period will be evaluated with a difference-in-difference (DID) approach to estimate HIV testing uptake and sexual/reproductive health services use. Primary and secondary outcomes will be measured at several

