Cluster randomized controlled trial: We will select up to 18 (2 pilot + 16 for full implementation) schools from the Urban District of Lusaka to receive the SKILLZ-Girl curriculum. Of the total (up to 18), half will be randomly allocated to host the standard SKILLZ-Girl curriculum, and the remaining half (e.g., up to eight) will be randomized to either enhanced SKILLZ-Club. Those schools randomized to standard SKILLZ Girl curriculum will only have access to SOC clubs. Those schools selected for enhanced SKILLZ Girl curriculum will offer SKILLZ Club. See **Figure 3** for study allocation flow.

Figure 3. School Selection Flow Chart

[figure not shown]
ONGOING REFERRAL TO COMMUNITY CARE FOR SERVICES

We anticipate that most of our evaluation cohort will not be HIV-infected. Thus, the retention to SRH analysis drives the sample size calculation of 351 girls using contraception at the end of two years, with, and risk ratio difference of 0.3 (30%) between the SOC and enhanced SKILLZ-Club schools. To realize the 351 needed to meet requirements for estimate sensitivity, we augment the initial sample size receiving the SKILLZ-Girl curriculum accounting conservatively for 25% uptake of SRH methods and multiplying by two to assess the difference within each SKILLZ-Girl model (phase 1) and accounting for attrition across the two years of follow-up (12.5%) resulting in a starting sample size of 3159 $((351/0.25) \times 2) \times 1.025$. **SKILLZ-CLUBS** will act as an extension to the SKILLZ-Girl curriculum enabling participants to seamlessly transition from the SKILLZ-Girl curriculum into the SKILLZ-Club. We anticipate minimal attrition (~15-20%). Participants will spend the majority of the study window in SKILLZ-Club and it is through the SKILLZ-Club affiliation that we will follow-up and ascertain outcomes for those enrolled longitudinally.

For the small minority of girls found to be HIV-infected across all schools where the study will be conducted, we will evaluate linkage to care and on treatment, VLS, and retention in care for a period of two years. These girls will be encouraged to continue on to the HIV positive-specific SKILLZ-Plus facility-based curriculum. We will quantitatively measure the impact of SKILLZ-Plus on linkage to care and treatment, retention and viral load at 6, 12, and 24 months after diagnosis (or since participant is identified by GRS as HIV+) using SmartCare data and compare to an existing matched cohort.

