Economic evaluation: We will assess cost-effectiveness in three steps. First, we will assess the net cost of the intervention and its consequences, using micro-costing and modeling techniques. Costs for the intervention itself will include mainly personnel to manage the intervention and the financial incentives. Costing of the intervention and control models will be captured in costing sheets that will be prepared before the start of the intervention aimed at capturing costs as they are spent; we will limit the costing from the provider perspective and will only limit costing to programmatic and not research costs. We will also cost the change in health care utilization precipitated by the intervention: both increased preventive care and decreases in curative care. This will be assessed combining utilization with standard values for unit cost (per MOH official records). Together, these generate net costs. Second, we will quantify the health benefits of the intervention, including health events (e.g., number and type of opportunistic infections, STIs) and Quality-Adjusted Life Years (QALYs) which translate morbidity in the short and long term (projected based on published longitudinal clinical studies) into a standard metric of health status. Health state utility data (for QALYs) will derive from studies in the literature. The analysis of expected costs and QALYs in the intermediate and long-term will be structured using a spreadsheet-based decision analysis created for this purpose in consultation with clinical experts. Third, we will calculate the economic outcome measures including the Incremental Cost-Effectiveness Ratio (ICER) and Return-on-Investment (ROI). The ICER is the ratio of net cost to health gain, comparing the SKILLZ-Plus to control (e.g., ICER for

HIV testing = $(C_{\text{intervention}} - C_{\text{control}}) / (\text{Testing rate}_{\text{intervention}} - \text{Testing rate}_{\text{control}})$, and is indicated if the intervention has a net cost (i.e., does not save money) while improving health outcomes (QALYs gained). All analyses will be repeated for 1, 2, 5, 10, & 20 years, and subjected to extensive sensitivity analyses to test the impact of uncertainty on results.

9. Ethical considerations

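### Aim 3 and question h promise cost-effectiveness of SKILLZ-Girl and of the whole Package with no comparator, but both arms receive SKILLZ-Girl, so the arms identify only the increment of the enhanced programme

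*Combined protocol and SAP*

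**What the plan says.** Section 7, Aim 3, sets out to "Estimate the short- and long-term cost-effectiveness and return on investment of the SKILLZ Girl, Club, and Plus curricula". Section 6, question h, asks "What is the short- and long-term cost-effectiveness of the SKILLZ Package intervention". The economic paragraph of Section 8a repeats the promise, including return on investment, for SKILLZ in general. None of the three names a comparator. Section 4 defines the Package broadly: "The SKILLZ Package entails three integrated programs that work together to build a continuous support system".

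The design is narrower. Section 4 sets the enhanced offering "compared to the SOC SKILLZ offering of SKILLZ-Girl only", and in Section 8c "half will be randomly allocated to host the standard SKILLZ-Girl curriculum" while the rest receive the enhanced version with SKILLZ-Club. SKILLZ-Plus is offered to HIV-positive girls in both arms, and its effect is assessed against matched SmartCare records (Sections 4 and 8f).

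Two places state a contrast that fits this design. Section 2b describes a "robust evaluation of effectiveness and cost-effectiveness (CE) between a standard SKILLZ- girl curriculum" and the enhanced approach. Section 8f says "Costing of the intervention and control models will be captured in costing sheets" and gives an example ICER for HIV testing as intervention minus control. The sentence that introduces that example, however, reads: "The ICER is the ratio of net cost to health gain, comparing the SKILLZ-Plus to control".

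**The concern.** A figure for the cost-effectiveness or return on investment of SKILLZ-Girl, or of the whole Package, needs an estimate of what would happen without it. No arm or cohort supplies one. The gap matters because the documents raise exactly that question. Section 1c says it is unclear whether the basic curriculum by itself changes health-seeking behaviour, and Section 5 says SKILLZ-Girl has not been rigorously evaluated for effectiveness or cost-effectiveness. Section 1c (purpose) and the text before it also tie the results to the two ministries and to integrating the Package into public education. An aim worded for the Package as a whole leaves open which question its figure answers.

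The ICER sentence adds to the ambiguity. It names SKILLZ-Plus, a programme for HIV-positive girls offered in both arms, and then illustrates the ratio with HIV testing rates by arm.

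**Working it through.** **Which contrast each promise needs, and what the study provides**

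| Target | Contrast needed | Provided? |
|---|---|---|
| SKILLZ-Girl (Aim 3) | SKILLZ-Girl against no SKILLZ-Girl | No: both arms receive a SKILLZ-Girl curriculum |
| SKILLZ-Club (Aim 3) | Club against no Club, same curriculum | Only bundled with the enhanced curriculum and event services |
| SKILLZ-Plus (Aim 3) | Plus against no Plus, in HIV-positive girls | Yes, non-randomised: matched SmartCare cohort |
| Whole Package (question h) | Package against no Package | No |
| Enhanced against standard (Section 2b) | Enhanced arm minus SOC arm | Yes: the trial arms |

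**Could another part of the plan fill the gap?** The baseline survey does not. Difference-in-difference (Section 8f) removes time trends through the control arm. For SKILLZ-Girl itself the control arm is treated, so change within it mixes the curriculum with ageing and with secular trends in testing, which Section 8f itself mentions. The decision model does not either. It takes utilities and long-term projections from published studies, but names no comparator without SKILLZ and no outside effect estimate for SKILLZ-Girl.

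**The plan's own calculation concerns the increment.** Inputs from Section 8c: uptake 60% (control) and 80% (intervention), alpha 0.05, power 80%, ICC 0.1, about 100 girls per school, up to 18 schools. I take the test as two-sided, with pooled variance and no continuity correction.

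- Per arm under individual randomisation: n = [1.96 × √(2 × 0.7 × 0.3) + 0.842 × √(0.6 × 0.4 + 0.8 × 0.2)]² / 0.2² ≈ 81.2, rounded up to 82.
- Design effect: 1 + (100 - 1) × 0.1 = 10.9.
- Girls per arm: 82 × 10.9 = 893.8, or 8.94 schools, rounded up to 9. That makes 18 in total, as planned. Power with 9 per arm is 80.7%.

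The stated number of schools is reproduced. It is sized for a 20-point difference between two SKILLZ arms.

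**How far the targets could differ (illustration only).** The testing ICER denominator from the arms is 0.80 - 0.60 = 0.20. Uptake without any programme is not observed, so it must be assumed. I use two figures in the documents: 13%, the baseline in internal programme data (Section 8c), and 47.5%, the share of girls aged 15-19 who had tested and learned their result (Section 1a).

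| Assumed uptake without programme | Standard SKILLZ-Girl against nothing | Enhanced programme against nothing | Latter ÷ 0.20 |
|---|---|---|---|
| 13% | 0.60 - 0.13 = 0.47 | 0.80 - 0.13 = 0.67 | 3.35 |
| 47.5% | 0.60 - 0.475 = 0.125 | 0.80 - 0.475 = 0.325 | 1.63 |

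These are denominators only. Against nothing, the numerator would also take in the full cost of SKILLZ-Girl, and the documents give no unit costs from which to work out the ICER itself.

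**The case against.** The best defence is that the operative text is already right. Section 8f costs an intervention and a control model and subtracts one from the other, and Section 2b frames cost-effectiveness as standard against enhanced. The documents also use SKILLZ as shorthand for the arm contrast: Aim 1 speaks of the impact of SKILLZ and then defines it as intervention against control schools, and Section 4 calls both arms versions of the Package. On that reading Aim 3 is loosely worded and nothing more. Much of this stands: the planned contrast between arms is sound. It does not settle the matter, because Aim 3 lists SKILLZ-Girl by name, neither Aim 3 nor question h states a comparator, and the ICER sentence points to a different programme from the one in its example.

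Three stronger readings are tempting, and the documents do not support them.

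- A reader might infer that the trial will report an uncontrolled before-after change as the value of SKILLZ-Girl. No section plans such an estimate.
- A reader might infer that the ICER would be wrong more than threefold. The 3.35 is the top of an assumed range. It subtracts a baseline for youth served by the implementing partner from planning assumptions for this cohort, and it ignores the cost numerator.
- A reader might infer that nothing in Aim 3 beyond the arm increment can be estimated. SKILLZ-Plus can be, subject to the matching assumptions, in HIV-positive girls.

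**Conclusion.** The point holds as a mismatch between a stated aim and the design. The two arms identify the joint increment of enhanced SKILLZ-Girl plus SKILLZ-Club over standard SKILLZ-Girl plus SOC clubs. The matched cohort separately addresses SKILLZ-Plus. Neither source, nor both together, gives the cost-effectiveness or return on investment of SKILLZ-Girl itself or of the whole Package. This rests on the composition of the arms, not on any numerical assumption. The possible size, 1.6 to 3.4 times the 20-point contrast on the effect side, depends on assuming 47.5% to 13% uptake without a programme. It shows only that the choice of comparator is not a detail. The planned calculation between arms needs no change.

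**What to change.** Restate Aim 3, question h, the economic paragraph of Section 8a and the ICER sentence of Section 8f as two comparisons:

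1. Incremental cost-effectiveness and return on investment of enhanced SKILLZ-Girl plus SKILLZ-Club over standard SKILLZ-Girl plus SOC clubs, from the trial arms, with HIV testing as an example outcome.
2. SKILLZ-Plus against its matched SmartCare cohort, on linkage, retention and viral suppression, described as non-randomised and limited to HIV-positive girls.

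Drop any figure for SKILLZ-Girl itself or for the whole Package. If the ministries need one, label it as modelling outside the trial comparison and specify in advance the source of the no-programme comparator and a sensitivity range.

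The change is to wording, and no additional data are needed. The price is a narrower claim: the trial would not be presented as showing whether the basic curriculum is worth its cost.

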Economic evaluation: We will estimate the short- and long-term cost-effectiveness and return on investment of SKILLZ for improving health outcomes for adolescent girls.

Figure 2. Evaluation enrolment flow

b. Study site and population/Research materials

Lusaka is the capital and the most inhabited city in Zambia. Home to 2 million people, it has the highest HIV prevalence at 14%⁴. The study will take place across all the highly densely populated areas of Lusaka where

[figure not shown]
CIDRZ supports government MoH clinics with ARV services, electronic data management, and youth-friendly trained clinical personnel, and where GRS has been implementing their basic curriculum and events. All schools selected will be secular government schools. Approximately 80% of school-age girls are reported to be in school in Lusaka. To facilitate the evaluation of SKILLZ, all girls enrolled in up to 18 government secondary schools in Urban Lusaka that GRS currently serves will be eligible to participate in the SKILLZ program and will be randomly allocated to either the enhanced or SOC SKILLZ implementation. For measuring impact, only girls aged 16 and over enrolled in Grade 10 at the start of the intervention period will be surveyed and followed because youth aged 16 and over can consent for SRH/HIV services without additional parental permission⁵⁵. (See *Section 9: Ethical Considerations* for details on waiver of parental consent).

c. Selection of participants, sampling methods and sample size

Study Population: In each school, we will recruit all girls in Grade 10 who are at least 16 years old at the start of the intervention period (i.e., the commencement of SKILLZ-Girl). Of the 30,000 youth in Lusaka that have benefitted from GRS services to date, GRS has seen HIV testing uptake of 62% as compared to a baseline of 13% (internal program data). We have powered the sample for our primary endpoints in Aim 1ii to account for attrition anticipated along the cascade (see below). For HIV testing, all eligible girls (estimated to be an average of 100 girls per school) in up to 18 schools is large enough to detect a significant difference in testing uptake if setting statistical significance at $\alpha=0.05$, $\beta=0.2$, ICC=0.1, and an expected testing uptake of 60% (control) and 80% (intervention).

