Difference-in-difference model. The primary outcome is the probability of testing for HIV at any time during the period when SKILLZ is delivered through to 24 months after the final soccer event. The primary analysis for Aim 1 will follow a difference-in-difference (DID) effect between study arms. The outcome of interest will be regressed on an indicator of study arm assignment interacted with a dichotomous variable POST which indicates the outcome after the intervention is implemented; this differentiates baseline and end-line for each study arm, controls for any time dependent variables that might confound the effect, as well as any time-invariant observed or unobserved confounders that might differ between study arm schools. Because of this, the DID is robust to time-invariant unobservable confounders (e.g., school quality) and time trends (e.g., secular increase in testing). Our estimator relies on the assumption of common time trends across intervention and control in absence of the intervention, and of static population. Additionally, we control for baseline individual and school-level moderators that may be unbalanced at baseline after randomization. School-level controls include size, promotion rates, sex composition and repetition and dropout rates (available in the district education office) and individual girls' controls include age, grade, maternal education, HIV knowledge. Clustering by school will be accounted for by a generalized estimating equation approach. We will estimate intention-to-treat (ITT) by including all girls in the evaluation cohort assigned to each arm rather than all girls who actually participated in SKILLZ.

Individual-level matched cohort analysis for HIV-infected: The analysis will follow an individual ITT estimator among individuals found to be HIV-infected, who will then be matched (based on clinic, age, ART state date, and gender) to HIV-infected individuals in the SmartCare database. The outcomes are the proportion of enrolled HIV+ girls who linked to care, who are virally suppressed and retained in care at 6, 12, and 24 months after diagnosis of HIV+ (using national electronic HIV medical record data). We will conduct an ITT analysis for the logistic probability of being suppressed at 6, 12, and 24 months after HIV+ diagnosis, where girl is the unit of analysis. All data will be analyzed using STATA.

Process evaluation: This will involve quantitative and qualitative analyses:

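### The stated 80% power for HIV testing holds only with all 18 schools and a large-sample z test; with a t reference it is about 77%, and the number of schools analysed is left unsettled

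*Combined protocol and SAP*

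**What the plan says.** Section 8c gives the power statement for HIV testing. All eligible girls, averaging 100 per school, "in up to 18 schools is large enough to detect a significant difference in testing uptake", with alpha 0.05, beta 0.2, ICC 0.1 and an "expected testing uptake of 60% (control) and 80% (intervention" arm). It gives no formula, reference distribution or sidedness.

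The number of schools is described in several ways:

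- Section 7, Aim 1: "9 SKILLZ control schools compared to 9 schools where enhanced SKILLZ will be delivered". Section 8a likewise has up to nine per arm.
- Section 8c, cluster randomized trial paragraph: "We will select up to 18 (2 pilot + 16 for full implementation) schools from the Urban District of Lusaka".
- The same paragraph: "Of the total (up to 18), half will be randomly allocated to host the standard SKILLZ-Girl curriculum", and then "the remaining half (e.g., up to eight) will be randomized".
- Section 4: up to 16 schools in each of the two arms.

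Section 8f plans a difference-in-difference regression with GEE for clustering by school, adjusted for individual and school characteristics. It names no small-sample correction.

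**The concern.** With 16 to 18 schools, the number of clusters governs both the precision of the comparison and the reference distribution for the test. A z test on an uncorrected GEE sandwich variance tends to reject too often when clusters are this few. A t reference or a bias-corrected variance restores the 5% level but costs power. If the planned 80% relies on the z reference, alpha 0.05 and beta 0.2 are not met together.

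The calculation also has almost no margin in the number of schools, yet the protocol does not say how many will be analysed. HIV testing is the primary outcome, so this figure will be used to judge how much weight a null result can bear.

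**Working it through.** **Inputs (Section 8c):** p1 = 0.60, p2 = 0.80, m = 100 girls per school, ICC = 0.1, alpha = 0.05. Two-sided testing is assumed, since sidedness is not stated.

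**Design effect:** 1 + (m − 1) × ICC = 1 + 99 × 0.1 = 10.9.

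**Reproducing the stated figure, k = 9 per arm**

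- Effective n per arm = 900 / 10.9 = 82.6.
- SE = sqrt[(0.6 × 0.4 + 0.8 × 0.2) / 82.6] = sqrt(0.40 / 82.6) = 0.0696.
- Difference / SE = 0.20 / 0.0696 = 2.87.
- z power = Φ(2.87 − 1.96) = 82.0%. It is 80.7% with a pooled variance under the null only, and 80.1% with a pooled variance throughout.
- In reverse: the standard two-proportion formula needs 82 per arm, and 82 × 10.9 / 100 = 8.94, which rounds up to nine schools per arm.

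So the stated 80% is recovered, and nine per arm is the minimum under this method. A one-sided test would give 88.3%, which does not match. The z reference is therefore an inference from the match; the protocol does not state it.

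**Changing one thing at a time (unpooled variance)**

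With k = 8, effective n = 800 / 10.9 = 73.4, SE = sqrt(0.40 / 73.4) = 0.0738 and the ratio is 2.71. The t column uses the noncentral t with 2k − 2 df.

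| Schools | z power | t power | Detectable difference from 60% at 80% power (t) |
|---|---|---|---|
| 18 (9 per arm) | 82.0% | 77.0% (16 df) | about 21 points |
| 16 (8 per arm) | 77.3% | 71.2% (14 df) | about 22 points |

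With a pooled variance, the t figures are 75.0% (18 schools) and 69.1% (16). The other z forms for 16 schools give 75.3% and 75.8%.

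- The t reference alone, keeping all 18 schools, takes power from 82% to 77%.
- Dropping the two pilots alone, keeping z, takes it from 82% to 77%.
- Both together give 71%.
- Taken literally, 16 schools per arm (Section 4) would give about 96% (t).

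**Attrition and more girls.** Applying the 12.5% attrition that Section 8c uses for the contraception calculation (87.5 girls per school) changes little: 76.5% (18 schools, t) and 70.7% (16, t). Spreading the 3,200-girl survey target of Section 8d over the schools gives about 178 per school and 78% (18, t), or 200 per school and 73% (16, t). The number of schools is the binding quantity.

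**The case against.** The strongest reply is that the protocol's arithmetic is correct: its own inputs give 80 to 82%. That stands. The finding is that the figure depends on a large-sample reference and on all 18 schools counting.

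Several stronger readings are tempting, and the documents do not support them.

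- **That true power is 71%, or the type II risk 29%.** This requires the pilots to be left out. No text excludes them. Section 8b allocates up to 18 schools at random, Section 8c halves the full total, and Sections 7 and 8a compare nine with nine. The main contrary sign is the aside about up to eight enhanced schools. The school selection flow chart (Figure 3) is not available here, so it cannot settle the matter.
- **That the planned covariates lower power further.** Section 8f says: "School-level controls include size, promotion rates, sex composition and repetition and dropout rates (available in the district education office"). These use degrees of freedom but may also explain between-school variance. The residual ICC is unknown, so the direction of the net effect is unknown.
- **That the 60% control rate is too low and power collapses.** Section 5 reports that "68.5% of girls that participated in the SKILLZ-Girl program underwent testing for HIV at the conclusion of the school-based curriculum", and Section 8c cites 62% from programme data. Holding the enhanced arm at 80% with control at 68.5% gives 32% power (16 schools, t). Keeping the 20-point difference (68.5% against 88.5%) gives 81%. The first source is a South African study by its reference title, and both arms accrue tests for 24 months, so neither scenario can be preferred.
- **That unequal school sizes cost a known amount.** They would lower power, but the documents give no spread.

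It also stands that a two-proportion calculation only approximates the adjusted difference-in-difference GEE, whose power cannot be computed from the stated inputs.

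**Conclusion.** The point holds in a limited form. On the plan's own rates, cluster size and ICC, power is about 77% rather than 80% once the small number of clusters is allowed for, even with all 18 schools. That is a type II risk of about 23% instead of 20%. If the primary analysis uses only the 16 full-implementation schools, power is about 71%; whether it does is an open question in the text.

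The figures assume two-sided testing, equal school sizes of 100, equal allocation, and a comparison of proportions in place of the planned model. The shortfall with 18 schools is modest. The inconsistent school counts matter more, because the answer ranges from about 71% to about 96% depending on which section is followed.

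**What to change.** In Section 8c, state whether the two pilot schools are randomised with the others and enter the primary analysis. Give one number of schools per arm, and carry it through Sections 4, 7, 8a and 8c.

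In Section 8f, specify GEE inference suited to few clusters: a t reference with cluster-based degrees of freedom, or a bias-corrected variance.

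Restate the power with its method and sidedness. For 60% against 80% with a t reference, this is about 77% with 18 schools (80% power for about 21 points) or about 71% with 16 (about 22 points). Any sensitivity table for control rates of 60 to 70% should show both a fixed enhanced rate and a fixed 20-point difference. Any allowance for covariates should show a range of residual ICC.

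The cost is text and a slightly less favourable power figure. No extra schools are needed.
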